## 8.0 CLINICAL TRIAL POPULATION

### 8.1 Number of Patients

Assuming a screening failure rate of 10%, a total of approximately 340 patients will be screened. Assuming an attrition rate equal to 15% a total of approximately 306 patients will be randomized (153 in the safinamide and 153 in the placebo groups).

Approximately 35 study centres will participate in the study. The enrolment will be competitive among sites.

The sample size calculation is described in [Section 20.3](#).

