### **Clinical Global Impression (CGI)**

The CGI (22) is the general name for 2 scales, the CGI-Severity scale (CGI-S) and the CGI-Change scale (CGI-C). The CGI-S scale measures global severity of illness at a given point in time. It will be rated on a 7-point Likert-type scale ranging from 1 (normal, not ill at all) to 7 (extremely severe). The CGI-S will be assessed at all visits, starting at baseline. The CGI-C scale will measure the change in the patient's clinical status from baseline using a 7-point scale, ranging from 1 (very much improved) to 7 (very much worse), with a score of 4 indicating no change. The change from the patient's baseline condition will be assessed by the Investigator at all post-baseline visits. In completing the CGI-C, the rater will review all efficacy-related data, and assess its clinical meaningfulness.

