## **20.3 Sample Size**

Sample size was computed through a Monte Carlo study with 1000 runs and using a Fixed Sequence Procedure (25) to account for multiplicity over the study primary endpoint (change from baseline to week 16 in the mean total daily “OFF” time) and the key secondary endpoint (change from baseline to week 16 in pain severity, as assessed by an 11-point Numerical Rating Scale - NRS). The Fixed Sequence Procedure implies that the key secondary endpoint will be testable provided that the primary endpoint has achieved statistical significance with a two-tailed p-value  $\leq 0.05$ .

Based on the Monte Carlo simulation it was estimated that a total sample size of 260 patients (130 in the safinamide and 130 in the placebo groups) ensures 90% power to detect a mean difference in the ‘off’ time at least 0.9 h between the safinamide and placebo groups with a two-sided significance level (alpha) of 0.05 using a two-sample t-test and assuming standard deviations of 2.35 for safinamide and 2.06 for placebo. Effect size and standard deviation estimates used in sample size computations are gathered from the Settle Statistical Report (Table 15.2.13).

Moreover, the same Monte Carlo study showed that the total sample size of 260 patients would also permit a marginal power equal to 88% to detect 1 point treatment difference in the NRS between the safinamide and placebo groups with a two-sided significance level (alpha) of 0.05 using a two-sample t-test and assuming a pooled standard deviations of 2.0. Standard deviation was estimated on the basis of previous post-hoc analyses of pain (25) whilst a 1 point treatment difference is considered to be a clinically meaningful treatment effect (26).

Assuming an attrition rate equal to 15% a total of approximately 306 patients will be randomized (153 in the safinamide and 153 in the placebo groups). The sample size calculations were performed using the Mediana package (27).

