## **20.4 Statistical Analyses**

### **20.4.1 General Statistical Considerations**

All data captured on eCRFs will be available as listings.

The statistical analysis will be performed by the CRO. If not otherwise stated all statistical analyses and data tabulations will be produced using SAS® for Windows release 9.4 (64-bit) or later (SAS Institute Inc., Cary, NC, USA).

Unless stated otherwise, all available data from withdrawn subjects will be included in the analysis up to the time of withdrawal.

The primary study objective will be assessed by testing the superiority of Safinamide compared to placebo and will be achieved if the analysis on primary end-point will be found statistically significant. The key secondary objective will be always assessed through a superiority analysis of Safinamide compared to placebo and, similarly, will be reached if the analysis on key secondary end-point will be found statistically significant. Conversely, the analyses on the remaining secondary efficacy endpoints will be treated as non-key secondary objectives since they will be performed only to support primary endpoints findings.

All tests will be two-sided and performed at the significance nominal level of  $\alpha = 0.05$ . Details are reported in Section 20.4.5.

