#### **20.4.3.3 Analyses of Other Secondary Endpoints**

- Change from baseline to week 16 in the mean total daily “ON” time, as assessed by 24-hour patient diary cards: the hypothesis of superiority of safinamide compared to placebo will be assessed using an ANCOVA model parameterized as above (i.e. as for the primary and key secondary endpoint), with point estimate of treatment differences reported as Least-Square Mean with associated two-tailed 95% confidence intervals and two-sided p-value.
- Change from baseline to week 16 in the mean daily “ON” time with no/non-troublesome dyskinesia, as assessed by 24-hour patient diary cards: the hypothesis of superiority of safinamide compared to placebo will be assessed using an ANCOVA model parameterized as above, with point estimate of treatment differences reported as Least-Square Mean with associated two-tailed 95% confidence intervals and two-sided p-value.
- Change from baseline to week 16 in the UPDRS total score during the “ON” phase: the hypothesis of superiority of safinamide compared to placebo will be assessed using an ANCOVA model parameterized as above, with point estimate of treatment differences reported as Least-Square Mean with associated two-tailed 95% confidence intervals and two-sided p-value..
- Change from baseline to week 16 in the UPDRS part II (ADL) score during the “ON” phase: the hypothesis of superiority of safinamide compared to placebo will be assessed using an ANCOVA model parameterized as above, with point estimate of treatment differences reported as Least-Square Mean with associated two-tailed 95% confidence intervals and two-sided p-value.
- Change from baseline to week 16 in the UPDRS part III (motor function) score during the “ON” phase: the hypothesis of superiority of safinamide compared to placebo will be assessed using an ANCOVA model parameterized as above, with point estimate of treatment differences reported as Least-Square Mean with associated two-tailed 95% confidence intervals and two-sided p-value.
- CGI-S score assessed at week 16: the hypothesis of superiority of safinamide compared to placebo will be assessed using the Wilcoxon-Mann-Whitney test stratified by centre, whilst point estimate of treatment differences will be reported as Hodges-Lehmann estimators together with associated two-sided nonparametric 95% confidence intervals.

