- Change from baseline to week 16 in the CGI-C: the hypothesis of superiority of safinamide compared to placebo will be assessed using the Wilcoxon-Mann-Whitney test stratified by centre, whilst point estimate of treatment differences will be reported as Hodges-Lehmann estimators together with associated two-sided nonparametric 95% confidence intervals.
- Change from baseline to week 16 in the PDQ-39 score: the hypothesis of superiority of safinamide compared to placebo will be assessed using an ANCOVA model

parameterized as above, with point estimate of treatment differences reported as Least-Square Mean with associated two-tailed 95% confidence intervals and two-sided p-value.

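### On the 7-category CGI scales the planned Hodges-Lehmann shift can in practice show only 0 or a full category, and its interval will usually include 0 even when the Wilcoxon test is significant

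*Protocol*

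**What the plan says.** Section 10.1.6 (Clinical Global Impression) defines CGI-S as a "7-point Likert-type scale ranging from 1 (normal, not ill at all) to 7 (extremely severe" and CGI-C as a "7-point scale, ranging from 1 (very much improved) to 7 (very much worse), with a score of 4 indicating no change".

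For severity, section 20.4.3.3 states: "CGI-S score assessed at week 16: the hypothesis of superiority of safinamide compared to placebo will be assessed using the Wilcoxon-Mann-Whitney test stratified by centre". CGI-C gets the same test. For both, the "point estimate of treatment differences will be reported as Hodges-Lehmann estimators together with associated two-sided nonparametric 95% confidence intervals". Section 20.4.3.3 names no other between-group measure for CGI. Centre is attached to the test; the text does not say whether it also enters the estimate.

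Three other places set the context. Section 20.4.3 plans counts, percentages, means, standard deviations, medians and quartiles by arm and time point for every efficacy endpoint. Section 20.4.1 treats these endpoints as support for the primary result. Section 20.4.5 leaves them without multiplicity adjustment.

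**The concern.** The Hodges-Lehmann estimate is the median of all safinamide-minus-placebo differences. It is meant for a location shift of an outcome that is at least roughly continuous. With whole-number scores every difference is a whole number and a large share are ties, so an effect between 0 and one category cannot be expressed. The Wilcoxon test does respond to such effects, because it gives half credit to ties.

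The clinical report could therefore print a p-value below 0.05 beside a difference of 0 (95% CI -1 to 0) for the two global ratings that are meant to back up the OFF-time result. A reader may discount the finding or suspect an error, and a measure substituted after unblinding would be post hoc. Because the protocol itself names the estimator, this is not a matter left open for the SAP.

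**Working it through.** **The plan's own figure.** The protocol gives no planning values for CGI, so its primary-endpoint calculation (section 20.3) serves only to fix arm sizes and a reference effect. Root-mean-square SD = sqrt((2.35² + 2.06²)/2) = 2.21. Standardised difference d = 0.9/2.21 = 0.41. With 130 per arm, SE = 2.21 × sqrt(2/130) = 0.274, and power = Φ(0.9/0.274 − 1.96) = 90.7% (90.5% by t-test), against 90% stated. Randomised total: 260/0.85 = 306, or 153 per arm. Both reproduce.

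**Why test and interval part company.** The standard interval takes the ordered pairwise differences at ranks mn/2 ± 1.96 × sqrt(mn(m+n+1)/12).

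- 153 per arm: mn = 23,409; half-width = 1.96 × 773.9 = 1,516.8 ranks, or 6.5% of pairs.
- 130 per arm: mn = 16,900; half-width = 1.96 × 606.3 = 1,188.3 ranks, or 7.0% of pairs.

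Lower scores are better on both scales. With 153 per arm, the upper limit falls below 0 only if safinamide is strictly better in more than 56.5% of pairs. The unstratified Wilcoxon test, before tie correction, is significant once wins plus half the ties exceed the same 56.5%. The gap between the two conditions is half the tie share.

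**Worked example (assumed).** Take a placebo CGI-C distribution of 1/8/27/42/16/5/1% over categories 1 to 7, with cumulative odds multiplied by the odds ratio (OR) for safinamide.

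| OR | Wins | Ties | Losses | Wins + half ties |
|---|---|---|---|---|
| 1.8 | 45.0% | 27.5% | 27.5% | 58.75% |
| 2.5 | 50.3% | 26.4% | 23.3% | 63.5% |

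At both ORs the expected test statistic is beyond its threshold (58.75 and 63.5 against 56.5), while wins alone are well short of 56.5%. The lower limit reaches -1 once wins exceed 50 − 6.5 = 43.5%, so the expected interval is -1 to 0. The median passes from 0 to -1 only when wins exceed 50%: not at OR 1.8, and only just at OR 2.5.

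**Simulation, proportional-odds model.** Same distribution, 130 or 153 per arm, 35 centres, centre-stratified (van Elteren) test at two-sided 0.05, pooled estimate, significant trials only:

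- OR 1.5 to 1.8: interval includes 0 in 100%; estimate is 0 in 88 to 96%.
- OR 2.5: interval includes 0 in about 97% (repeat runs 95 to 96%); estimate is 0 in 45 to 49%.

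**Simulation, rounded-normal scores.** d = 0.41, 35 centres, significant stratified test. Each cell shows 130 / 153 per arm.

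| Score SD (assumed) | Estimate 0 | Estimate -1 | Interval includes 0 | Win-probability interval excludes 0.5 |
|---|---|---|---|---|
| 0.7 | 98.1 / 98.9% | 1.9 / 1.1% | 100 / 100% | 97.8 / 98.8% |
| 0.8 | 92.8 / 95.3% | 7.2 / 4.7% | 100 / 100% | 98.8 / 98.5% |
| 1.0 | 70.4 / 75.3% | 29.6 / 24.7% | 99.4 / 99.8% | 97.8 / 98.8% |
| 1.2 | 43.3 / 45.5% | 56.4 / 54.5% | 97.3 / 97.2% | 98.9 / 99.1% |

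The win probability here is P(safinamide better) + 0.5 × P(tie), pooled over centres; its mean in these runs was about 0.61. With larger effects the interval problem eases: it includes 0 in 89 to 100% of significant runs at d = 0.5 and in 67 to 99% at d = 0.6.

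**The case against.** The strongest objection is that the protocol never says the estimate is pooled. If centre means are subtracted before the differences are taken, the differences are no longer whole numbers. With the same assumed CGI-C distribution and 153 per arm, that centre-aligned version gave an estimate of exactly 0 in none of the significant trials. Its interval included 0 in 10% at OR 1.8 and 1% at OR 2.5. This stands as far as it goes: the text is compatible with that reading. But it is a non-standard form, nothing in section 20.4.3.3 points to it, and using raw differences within centres would still give whole numbers.

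Two further objections hold. Section 20.4.3 will show the full category distribution and the means by arm, so size and direction can be read off descriptively. And both endpoints lie outside the fixed sequence, so no confirmatory claim, power figure or type I error depends on them.

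A reader might infer more than the documents support:

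- That the point estimate will nearly always be 0. This holds only for tightly clustered scores (SD about 0.8 or less) and effects up to about 0.4 SD; otherwise it often jumps to -1.
- That the estimator ignores centre. The text is silent.
- That the interval contradicts the test. An interval of -1 to 0 touches 0 at its end because the scale is coarse; it does not favour the opposite conclusion.
- That the report will contain no effect size. The descriptive summaries remain.

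**Conclusion.** The point holds as a minor improvement to two supportive endpoints. With the standard pooled computation, the prespecified effect measure cannot resolve anything between no difference and a full category. For small to moderate effects its interval will include 0 in nearly every significant result. The interval finding is stable across the two models for moderate effects; the behaviour of the point estimate is not, and depends strongly on the spread of the scores.

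The figures rest on assumptions that the protocol does not supply: the CGI distributions (SD 0.7 to 1.2, or the stated placebo percentages), effects of d 0.25 to 0.6 or OR 1.5 to 2.5, patients spread evenly over 35 centres, and an estimate not aligned by centre. The arithmetic reason, that ties count half in the test and not at all towards moving the interval off 0, does not depend on them.

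**What to change.** In section 20.4.3.3, keep the centre-stratified Wilcoxon-Mann-Whitney test for CGI-S and CGI-C. Replace the Hodges-Lehmann shift with the Mann-Whitney win probability (safinamide better, plus half the ties), or the equivalent win odds, with a 95% confidence interval. State that it is stratified by centre, with small centres pooled by a rule fixed before unblinding. Section 20.4.6 already describes blinded pooling by enrolment and geography for the interaction analysis, and could be extended to this use.

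A proportional-odds model with one term per centre is not a good substitute. 306 patients over about 35 centres is 306/35 = 8.7 per centre, spread over seven categories; such a model would need pooled centres as well. If the Hodges-Lehmann shift is kept alongside, say whether it is pooled or centre-aligned.

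The cost is one sentence in the protocol and SAP and one changed table. The downsides are a less familiar effect measure and the need to pool sparse centres. The simulated win probability was pooled, so how closely a stratified interval agrees with the stratified test should be checked when the SAP is written.

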#### **20.4.4 Handling of missing data**

Missing data on the primary and key secondary efficacy endpoints will be imputed using multiple imputation (MI) as the primary imputation method and last observation carried forward (LOCF) as sensitivity analysis. Missing data on all the other secondary efficacy endpoints will be imputed only using LOCF method. Details regarding the multiple imputation approach (i.e. number of imputations, the randomization seed and the imputation and analysis models that will be used) will be reported in the SAP.

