### **4.5 Discussion of Study Design**

This is a Phase III, multicentre, randomised, double-blind, placebo-controlled study to evaluate the effects of 100 mg safinamide, administered orally once daily (od), in Chinese PD patients, experiencing motor fluctuations while on stable doses of L-dopa (alone or in

combination with other anti-Parkinson drugs). Eligible patients are required to meet the United Kingdom PD Society Brain Bank Clinical Diagnostic Criteria (14).

The double-blind design is adopted to minimize systematic bias in ratings resulting from the knowledge of the treatment received. Randomization helps achieve statistical balance across the two treatment groups. The principal efficacy measure, i.e., the increase in mean daily “OFF” time during the 24-hr diary recording period, was chosen based on regulatory guidance and prior use in other trials in similar populations. Other efficacy measures (“ON” time, UPDRS, CGI, PDQ-39 and NRS) were selected based on the domains of symptoms affected in patients with PD. Tolerability was assessed by changes in laboratory evaluations, vital signs, 12-lead ECG, physical and neurological examinations, and adverse events.

The dose of safinamide (100 mg/day titrated from 50 mg/day after 2 weeks) was selected based on the results of the previous pivotal trials (in particular the study SETTLE), and according to the recommendations of the SmPC. The modulation of glutamate is maximized with the dose of 100 mg. Moreover, this is the dose that has shown to improve significantly dyskinesia (in moderate-severe dyskinetic patients) and PD non-motor symptoms such as chronic pain and mood deterioration. In the SETTLE study, the same dose of 100 mg/day has been administered to a cohort of 168 Asian-Pacific patients, reaching significant positive improvement of fluctuations and motor symptoms.

The study involves a placebo group. Placebo will be added to the standard stabilized treatment as a control of the safinamide group, hence patients on placebo will have benefit from other ongoing anti-PD medication. In addition, patients will be observed during the study more frequently than in the normal clinical practice and in case of any safety issue or lack of efficacy can withdraw from the study at any time.

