## 15.0 CLINICAL TRIAL WITHDRAWALS/ DROP-OUTS

Patients may be withdrawn from the study at their own request or at the discretion of the Investigator for one of the following reasons:

- Patient withdraws consent to participate.
- Pregnant female patients must be withdrawn from the study without delay. Follow-up should be performed in accordance with [Section 17.10](#).
- Patient has an AE that, in the opinion of the Investigator, requires the patient's discontinuation. Follow-up should be in accordance with [Section 17.9](#).
- Any clinically significant abnormal findings in physical examination, ECG, vital signs, haematology, chemical chemistry which, in the opinion of the Investigator may compromise the safety of the patient in the study or interfere with evaluation of the IMP or reduce the patient's ability to participate in the study.
- Intercurrent illness requiring pharmacological treatment with a non-permitted drug or a drug which interacts in any way with the test treatment or with study evaluations.
- Patient is non-compliant with the protocol.
- Continuation in the study would be detrimental to the patient's safety in the opinion of the Investigator.
- The Investigator or the Sponsor, for any reason, stops the study.
- Sponsor, CA, or EC terminate the trial at an individual site.

Patients who prematurely withdraw from the study while receiving study medication should complete the EOT Visit assessments, when possible. Patients must return the medications and details regarding AEs and concomitant medications will be collected.

Patients who are withdrawn from the study will not be replaced. In the event that a patient discontinues from the study prematurely due to an AE or SAE, they will be followed until the event has resolved (returns to normal or baseline values) or has stabilised.

The reason for withdrawal of a patient from the study or premature discontinuation of the treatment must be fully documented in the eCRF as well in source documents. Follow-up for withdrawn patients follows the procedures described in [Section 17.8](#) and [Section 17.9](#).

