#### **20.4.3 Efficacy Data**

The FAS population will be used for the primary analyses of each of the efficacy endpoints whilst results from supplemental analyses using the Per Protocol Population will be compared to those based on the FAS population to assess the effects of dropouts, missing data, protocol violations and deviations.

The distributions of all the efficacy endpoints listed in Section 20.2 will be summarized by treatment group and time point. Counts and percentages will be reported with the latest computed based on the numbers of patients with non-missing observations. The percentages will be suppressed when the count is zero in order to draw attention to the non-zero counts. Furthermore, efficacy endpoints will be further summarized by arithmetic means, standard deviations, medians quartiles, minima and maxima.

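### LOCF, the only imputation-based sensitivity analysis named for OFF time and pain NRS, does not probe departures from missing at random

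*Protocol*

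**What the plan says.** Protocol section 20.4.4 states that missing primary and key secondary data will be "imputed using multiple imputation (MI) as the primary imputation method and last observation carried forward (LOCF) as sensitivity analysis". The statistical summary in section 3.0 says the same. What goes to the SAP is limited to the MI specification: "Details regarding the multiple imputation approach (i.e. number of imputations, the randomization seed and the imputation and analysis models that will be used". The choice of LOCF as the sensitivity method is therefore fixed in the protocol.

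Other places bear on the point:

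- Section 20.4.3 says the per-protocol (PP) results will be "compared to those based on the FAS population to assess the effects of dropouts, missing data, protocol violations and deviations".
- Section 20.4.1 says that, unless stated otherwise, "all available data from withdrawn subjects will be included in the analysis up to the time of withdrawal".
- Section 4.5 says patients "in case of any safety issue or lack of efficacy can withdraw from the study at any time". Section 15.0 lists among the reasons for withdrawal "Intercurrent illness requiring pharmacological treatment with a non-permitted drug". Sections 9.2.2 and 11.2 have patients who cannot tolerate the lower dose leave the study.
- Sections 7.1, 9.2.3 and 15.0 ask withdrawing patients for the end-of-treatment or early-termination assessments, but only where possible. That visit includes diary review and the NRS.
- Section 20.3: "Assuming an attrition rate equal to 15% a total of approximately 306 patients will be randomized".

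**The concern.** Standard MI is valid if data are missing at random (MAR): given what was observed, a leaver's unseen week-16 value is distributed like that of a comparable patient who stayed. Section 20.4.4 does not state this assumption, and the protocol gives reasons to doubt it. Lack of efficacy and intolerance are expected routes out. For pain there is a direct link: opioids are non-permitted under section 11.1, so a patient whose pain worsens enough to need one may be withdrawn, and the week-16 NRS is then missing for a reason tied to the pain itself.

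A sensitivity analysis should vary the assumption on which the primary analysis rests. LOCF replaces it with a different fixed assumption. A patient who stopped safinamide keeps an on-treatment value as the week-16 outcome, and that value is treated as if it had been observed.

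At stake is how a positive result is read. A result that depends on optimistic outcomes for leavers could be reported as robust. Because section 20.4.5 tests pain only after OFF time succeeds, a fragile primary result would also carry the pain claim.

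**Working it through.** **Inputs (section 20.3).** Effect 0.9 h; SDs 2.35 and 2.06; 130 evaluable per arm; two-sided 0.05; attrition 15%; 153 randomised per arm.

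**The plan's own figures.** SE = sqrt((2.35² + 2.06²)/130) = sqrt(9.7661/130) = 0.274 h. Power by noncentral t is 0.905, against 90% stated. Randomised number: 260/0.85 = 305.9, so 306, as stated. Both reproduce.

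**Which SE applies.** The MI analysis runs on the FAS, up to 153 per arm, and adjusts for baseline. A simulation of MI with 153 per arm gave SE 0.235 h. Its assumptions are not in the protocol: SD 2.2, between-visit correlation 0.5 to 0.7, 15% leavers. Unadjusted with no missing data, 153 per arm would give sqrt(9.7661/153) = 0.253 h, so 0.235 h relies on some gain from adjustment. I use 0.274 to 0.235 h as a range.

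**Tipping shift.** If 15% of the safinamide arm is imputed and each imputed value is worsened by d hours, the arm mean moves by 0.15 × d. Holding the SE fixed, significance is lost at d = (observed − 1.97 × SE)/0.15.

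| Observed difference | SE 0.274 (threshold 0.540 h) | SE 0.235 (threshold 0.463 h) |
|---|---|---|
| 0.9 h | (0.9 − 0.540)/0.15 = 2.4 h | (0.9 − 0.463)/0.15 = 2.9 h |
| 0.65 h | (0.65 − 0.540)/0.15 = 0.7 h | (0.65 − 0.463)/0.15 = 1.25 h |

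**If leavers lose all benefit.** 0.9 × 0.85 = 0.765 h. Power = Φ(0.765/SE − 1.97):

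- SE 0.274: Φ(0.82) = 79%, against Φ(0.9/0.274 − 1.97) = 91% at the full 0.9 h.
- SE 0.235: Φ(1.29) = 90%, against Φ(0.9/0.235 − 1.97) = 97%.

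**The same arithmetic for the NRS** (SD 2.0, 130 per arm): SE = 2.0 × sqrt(2/130) = 0.248, threshold 0.489. The tipping shift is (1.0 − 0.489)/0.15 = 3.4 points if 1 point is observed, and (0.6 − 0.489)/0.15 = 0.7 points if 0.6 is observed.

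**Does LOCF respond to the threat?** A simulation used 306 patients, four post-baseline visits, visit correlation 0.6, 15% dropout per arm unrelated to outcome, and 600 trials per scenario. These are assumptions, not protocol figures.

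| Worsening of unseen safinamide outcomes | Full-data effect | MI | LOCF |
|---|---|---|---|
| none | 0.90 h | 0.90 h | 0.83 h |
| 0.9 h | 0.77 h | 0.90 h | 0.83 h |
| 2.0 h | 0.60 h | 0.90 h | 0.83 h |

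MI and LOCF do not move, because both use only what was seen. That follows by construction, and it is the point: only an analysis that puts the shift in explicitly can report its effect.

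**The PP comparison.** Section 20.4.2 defines PP by compliance and absence of major deviations. It does not require a week-16 value. If leavers were excluded as not having taken the drug as planned, the result would be close to a completers' analysis, which does not vary MAR either.

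**The case against.** A reader might infer that LOCF will almost always agree with MI and that the check is therefore empty. The documents do not support this. They say nothing about agreement, and in simulation LOCF moved the estimate by about 4% to 13%: 0.90 to 0.86 h or 0.83 h with equal dropout, depending on the assumptions, and 0.90 to 0.78 h in one run with 20% against 10% dropout. The significance verdict agreed in 97% of trials at a true effect of 0.9 h and in 92% at 0.5 h, where MI was significant and LOCF was not in 5.5%. LOCF carries some information. What it lacks is any link to how bad the unseen outcomes could be.

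A reader might also take the 79% power alone as the finding. It uses the unadjusted SE with 130 per arm, which is not the size of the MI analysis; with SE 0.235 h the figure is about 90%. Only the range can be defended.

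The early-termination visit is the best counter-argument. Where it takes place, the poor value that prompted withdrawal is recorded, MI can condition on it and LOCF carries it forward. This reduces the problem. It does not remove it, because the visit is obtained only when possible and shows nothing after withdrawal.

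It is also fair to say that 0.77 h is the right answer only if the question includes loss of benefit after stopping. For the effect under continued treatment, 0.90 h need not be biased. The protocol does not say which is meant.

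Finally, the SAP may add analyses, and section 20.4.2 lets it extend the PP criteria. That limits the point to what the protocol names.

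**Conclusion.** The point holds in a limited form. LOCF is the only imputation-based sensitivity analysis the protocol names for the two endpoints under type I error control. It does not probe departures from MAR, and neither does the PP comparison. The protocol gives plausible reasons for such departures and plans no outcome data after withdrawal.

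The consequence depends on the result. At an observed 0.9 h the conclusion would survive a shift of about 2.4 to 2.9 h in the safinamide dropouts. At 0.65 h a shift of about 0.7 to 1.25 h would overturn it, and neither planned check would report this. These figures assume 15% imputed in the safinamide arm, an SE between 0.274 and 0.235 h, and an SE unchanged by the shift.

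This is a worthwhile, inexpensive improvement. It does not show that the primary analysis is invalid.

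**What to change.** In section 20.4.4 and in section 3.0, keep MI as the primary method. Name as the sensitivity analysis, for both OFF time and NRS, a delta-adjusted tipping-point MI analysis in the safinamide arm, a reference-based MI analysis drawing on the placebo arm, or both. Keep LOCF as a supplementary table. One analysis of this kind is enough to meet the point.

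In section 20.4.3, stop presenting the PP-versus-FAS comparison as an assessment of missing data; it can stay as a check on deviations.

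If the SAP already contains such an analysis, only the protocol wording needs aligning.

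The cost is a wording change and extra imputation runs. Conduct and sample size are unaffected. The downside is that the reported sensitivity estimate may be less favourable than the one from LOCF.
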